3.6 Fluciclovine (¹⁸F) PET/CT

Fluciclovine (¹⁸F) is a synthetic amino acid ([¹⁸F]1-amino-3-fluorocyclobutane 1-carboxylic acid) developed by Shoup et al as a PET radiotracer for visualising malignant tumours [45]. The concept of using radiolabeled amino acids for the imaging of cancer is based on the increased metabolic demand of tumour cells, with enhanced channelling of amino acids into select metabolic pathways and increased expression of amino acid transporters to acquire these substrates. It is thought to be taken up by PCa cells via the ASCT2 and LAT1 amino acid transporters, and is not metabolised upon internalisation [46].

In 2007, Schuster et al first described the use of fluciclovine (¹⁸F) PET/CT in PCa in 15 patients with either primary disease or BCR [47]. This yielded promising findings of accurate nodal staging and identification of disease sites in patients with proven recurrence. This group have gone on to expand their work in a single centre study, evaluating the diagnostic performance of fluciclovine (¹⁸F) PET/CT compared to that of ¹¹¹In-capromab pendetide SPECT/CT in BCR. The latter is a radionuclide tracer licenced and established as standard of care for PCa imaging in the USA, but has been shown to have low sensitivities, with dismal detection of bone metastases [48]. Based on their latest published results in May 2014 from a cohort of 93 patients [49], fluciclovine (¹⁸F) PET/CT demonstrated a significantly higher accuracy, detecting more prostatic and extra-prostatic disease, and effectively up-staging 25.7% of cases. With specific regards to extra-prostatic disease (n=70), fluciclovine (¹⁸F) PET/CT detected disease in 18 more patients compared to ¹¹¹In-capromab pendetide (22 vs 4). Fluciclovine (¹⁸F) PET/CT had 55.0% sensitivity, 96.7% specificity,

72.9% accuracy, 95.7% positive predictive value (PPV) and 61.7% negative predictive value (NPV) compared to ¹¹¹In-capromab pentetide with 10.0%, 86.7%, 42.9%, 50.0% and 41.9%, respectively. Histological proof was obtained for majority (96.1%) of the lesions which had fluciclovine (¹⁸F) positivity.

In the largest cohort to date of intra-individual comparison of fluciclovine (¹⁸F) to ¹¹C-choline PET/CT, Nanni et al compared diagnostic performance between the two tracers in 28 patients with BCR after RP, in a single-centre study [50]. In the setting of relatively low PSA levels (mean 2.9 ng/mL, range 0.2- 14.6), the positive detection rate was found to be higher in fluciclovine (¹⁸F) compared to ¹¹C-choline PET/CT (35.7% vs 17.8%). Specifically, the detection rate was higher at PSA levels ≤ 1 ng/mL and > 2 ng/mL, and similar at levels between 1 – 2 ng/mL. All choline-positive lesions were also fluciclovine-positive. Fluciclovine (¹⁸F) PET/CT was positive in an additional 5 patients who had negative ¹¹C-choline PET/CTs. The tumour-to-background ratio (TBR) of fluciclovine (¹⁸F) was greater than ¹¹C-choline in 83.3% of lesions. There were also fewer false positive findings on fluciclovine (¹⁸F) PET/CT. Increased choline uptake by liver angiomas and several inflammatory inguinal lymph nodes were fluciclovine-negative. The same trend of higher detection rates across all PSA levels, and higher TBR in fluciclovine (¹⁸F) PET/CT compared to ¹¹C-choline PET/CT in a larger cohort of 50 patients was more recently presented by the same group [51].

Compared to its radiolabelled choline counterparts, fluciclovine (¹⁸F) also has a more favourable biodistribution. It has minimal renal excretion and associated bladder activity, and low homogeneous activity in the bowel [52]. Furthermore, being an ¹⁸F labelled tracer, it is a distributable product which does not have to be manufactured on-site.

With a high positive predictive value (95.7%) for extra-prostatic disease, almost entirely confirmed by histology, and a higher detection rate than choline, fluciclovine (¹⁸F) bears hallmarks of a competitively diagnostic agent in BCR. The impact of fluciclovine (¹⁸F) PET/CT on clinical management of patients with BCR remains to be defined, as is the PSA level associated with probability of a positive scan. Furthermore, the encouraging results on diagnostic performance observed at two expert centres need to be corroborated with larger multi-centre data, in order to formally validate its clinical utility for medical practice.

3.7 Proposed Research

In the setting of growing single-centre evidence of superior diagnostic performance of fluciclovine (¹⁸F) PET/CT in BCR, our primary aim is to assess its clinical impact on treatment decisions in a multi-centre study in patients with BCR being considered for radical salvage treatment (with curative intent). In addition, we aim to further characterise its diagnostic performance, afforded by larger numbers of patients from multi-centre recruitment. We also aim to assess the effect of PSA level on probability of lesion detection by fluciclovine (¹⁸F).

4. OBJECTIVES AND OUTCOME MEASURES/ENDPOINTS

Objectives	Outcome Measures/Endpoints

Primary Objective
 
To confirm the clinical benefit of fluciclovine (¹⁸F) PET/CT in affecting management decisions in patients with BCR being considered for radical salvage treatment (with curative intent).
	
The record of the revised management plan post fluciclovine (¹⁸F) PET/CT scan in comparison to the pre-scan intended management plan.

Secondary Objectives
 
 1. To assess possible improvement in outcome of radical salvage treatment based on fluciclovine (¹⁸F) PET/CT being included in the assessment. 2. To assess the prostate specific antigen (PSA) threshold for positive lesion detection by fluciclovine (¹⁸F) PET/CT in BCR 3. To assess the safety of fluciclovine (¹⁸F) injection in patients undergoing PET/CT 4. 	
 1. The proportion of patients who have a sustained response to radical salvage therapy. 2. PSA levels in relation to scan positivity will be analysed to determine the optimal PSA threshold for detecting recurrent PCa by fluciclovine (¹⁸F) PET/CT. 3. Safety will be assessed from data on the occurrence of adverse events (AEs) and changes in clinical laboratory tests, vital signs, injection-site status, and physical examination findings from the time of administration of fluciclovine (¹⁸F) injection throughout the study period. 4. .

5. STUDY DESIGN

5.1 Summary of Study Design

This will be an open-labelled, multi-centred study in the UK. The study group will include up to 180 patients with a diagnosis of BCR of previous radically treated PCa, and who are being considered for radical salvage therapy. Patients will have a fluciclovine (¹⁸F) PET/CT scan in addition to standard work-up for radical salvage therapy. The clinical utility of fluciclovine (¹⁸F) PET/CT will be assessed by recording changes to the recommended management plan influenced by the scan result.

Eligible patients who have expressed interest in the study will be provided detailed information about the study to consider participation, and means to communicate with the study team to discuss and raise any queries regarding participation. If the patient would like to take part, an enrolment visit (Visit 1) will be organised. Written informed consent, study registration and screening (including baseline blood tests and electrocardiogram [ECG]) will be performed on the same visit. The visit is also a further opportunity to ensure all queries about the study have been addressed.

[figure not shown]
At the baseline imaging visit (Visit 2), participants will undergo routine medical screening approximately 1 hour prior to receiving fluciclovine (¹⁸F) injection and undergoing PET/CT imaging. Vital signs and the

injection site will be monitored regularly for 2 hours after administration of fluciclovine (^{18}F). In the absence of AEs, patients may be discharged 2 hours after administration. Participants will receive a telephone consultation 24 -72rs after completion of fluciclovine (^{18}F) PET/CT to review any AEs that have occurred in the interim following discharge (Telephone Visit 3). Furthermore, participants will attend a subsequent hospital outpatient appointment (Visit 4) after the scan to discuss their test results and treatment options, and undergo post-imaging blood tests and ECG, during which they will have a further opportunity to report any AEs. Participants will receive a second telephone consultation 1 month after completion of fluciclovine (^{18}F) PET/CT to review any AEs that have occurred in the interim (Telephone Visit 5). Subsequent hospital visits for treatment and assessing response to treatment will be performed as part of routine standard of care.

Participation in Visit 1 should take 30 minutes to 1 hour. Visit 2 will take approximately 3 hours from the point of commencing medical screening to being discharged. Visit 4 will take approximately 30 minutes and may vary depending on practice of the participant's clinical team. Telephone consultations will take approximately 15 minutes.

In patients who receive radical salvage therapy (regardless of fluciclovine (^{18}F) PET/CT result), PSA should be assessed a maximum of 31 days before therapy and at least once between 7-8 months after treatment completion. Where possible, this should be arranged to coincide with treatment-associated hospital visits as per standard of care. If these cannot be incorporated into the hospital visits, a minimum of one, maximum of two extra visits will be required for these PSA tests.

5.2 Summary Flow Chart of Study Design

6. PARTICIPANT IDENTIFICATION

6.1. Study Participants

Participants with a diagnosis of BCR of previous radically treated PCa, aged ≥ 18 years old, being considered for radical salvage therapy (with curative intent).

6.2. Inclusion Criteria

- (1) The subject is a male ≥ 18 years old.
- (2) The subject has had an original diagnosis of PCa and underwent radical curative therapy at least 3 months before enrolment, and has been diagnosed with BCR on the basis of:
 - a. Post RRT / brachytherapy: Increase in PSA level ≥ 2.0 ng/mL above the nadir level after radiotherapy (RT) or brachytherapy (ASTRO-Phoenix criteria) [53], or
 - b. Post RP: EITHER two consecutive rises in PSA and final PSA > 0.1 ng/mL OR three consecutive rises in PSA. This definition is also applicable to subjects with PSA persistence post RP (where the PSA fails to fall to undetectable levels).
 - i. In addition, the subject post RP, should have a PSA doubling time of ≤ 15 months OR PSA level ≥ 1.0 ng/mL at time of recruitment. The PSA doubling time will be calculated using the Memorial Sloan Kettering Cancer Center nomogram (<http://www.mskcc.org/nomograms/prostate/psa-doubling-time>), based on a minimum of two PSA levels within 12 months of screening, taken after the last recorded nadir PSA available at time of screening.
- (3) The subject has not had previous recurrences of PCa, i.e. this is the first diagnosis of BCR.
- (4) The subject is being considered for radical salvage therapy.
- (5) The subject is able and willing to comply with study procedures, and signed, dated and timed informed consent is obtained before any study-related procedure is performed.
- (6) The subject's Eastern Cooperative Oncology Group [ECOG] performance status 0-2.
- (7) The subject should not have received androgen-deprivation therapy within 3 months of screening.
- (8) The subject has a normal or clinically acceptable medical history and vital signs findings at screening (up to 14 days before administration of study drug).

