In the same meta-analysis, PSA response following a change in treatment based on choline PET/CT results was evaluated using pooled data from 10 studies (n=404) [16]. This demonstrated 25% of patients having a complete PSA response. Treatments included salvage lymphadenectomy (LND) and pelvic radiotherapy.

Despite better diagnostic performance compared to conventional imaging, choline PET/CT still suffers from suboptimal sensitivity. Whenever choline-PET/CT identifies a suspected lesion, almost twice as many metastases are present [23], an observation reflected in data from recent meta-analyses. Von Eyben et al [16] pooled data from 11 studies (n=609) evaluating the performance of choline in detecting lymph node metastases in BCR – with histological correlation. Pooled sensitivity was 59% (51%–66%) and specificity was 92% (89%–94%). Hence, choline cannot adequately characterise the extent of nodal disease in BCR.

In the context of primary prostate cancer, Evangelista et al [24] pooled data from 10 studies (n=441) evaluating the performance of choline in detecting lymph node involvement. This also yielded a relatively poor pooled sensitivity of 49.2% (95% C.I., 39.9-58.4%), with a higher specificity of 95% (95% C.I., 92-97.1%).

While it performs better than conventional imaging counterparts, the detection rate of choline PET/CT remains poor in the setting of relatively low PSA and slow PSA kinetics. Husarik et al and Castellucci et al reported a moderate and low detection rate in case of PSA value <2 ng/mL and <1.5 ng/mL (71.4% and 28%), respectively [25, 26]. The detection rate of metastases has been described to range between 20% and 36% in patients with PSA <1 ng/mL, compared to 63%-83% where PSA levels exceed 3 ng/mL [27-29]. In a cohort of 109 BCR patients with negative conventional imaging (TRUS, MR, abdominopelvic CT, bone scintigraphy), Giovacchini et al reported a higher rate of positive ¹¹C-choline PET/CTs with higher PSA [17]. Imaging was positive in 3 of 65 (5%), 4 of 26 (15%) and 5 of 18 patients (28%) with PSA between 0.2 and 1, between 1 and 2, and greater than 2 ng/ml, respectively.

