7.5. Baseline Assessments

Visit 1 (after successful screening and patient informed consent obtained)

Demographics

The participant's age will be recorded.

Medical History

This forms part of the participant's routine clinical care, consisting of significant past medical history and drug history including known drug allergies.

PSA level

The dates and levels of the participant's PSA from the date of radical therapy will be recorded. These values will be obtained from the participant's hospital records. A repeat PSA level will be measured at time of screening at the same time as the clinical laboratory tests are taken.

PCa treatment history

Specific details on the treatment history for PCa will be recorded. This will include the date of initial PCa diagnosis, initial tumour stage and Gleason score, dates of radical treatment and adjuvant treatment (if given), date of BCR diagnosis. This information will be obtained from the participant's hospital records.

Imaging history

The nature, date and outcome of imaging examinations performed up to 3 months before screening will be recorded. This information will be obtained from the participant's hospital records.

Intended management plan

The management plan, based on pre-existing clinical information including results of conventional imaging, will be recorded. This information will be obtained from the participant's hospital records or MDT records.

ECG

An ECG will be performed.

Vital Signs

Sitting blood pressure and heart rate will be recorded.

Urine

Patients will be asked to provide a mid-stream specimen of urine to be tested with urine dipstick (leucocytes, nitrites, pH, protein, ketones, glucose, bilirubin, blood, urobilinogen). If the sample is positive for leucocytes or nitrites, the sample should be sent for urine microscopy and culture and if the

patient has symptoms of a urinary tract infection, this should be treated according to local guidelines prior to PET/CT. Fluciclovine (^{18}F) PET/CT can be performed during such treatment.

Clinical laboratory tests

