11.2. Analysis of Outcome Measures/Endpoints

Evaluable patients are those that have had all baseline study measures recorded, including having had a fluciclovine (¹⁸F) PET/CT scan.

Evaluation of fluciclovine (¹⁸F) PET/CT

Evaluation of the fluciclovine (¹⁸F) PET/CT images will be primarily reviewed by site-based investigator(s) (as per standard of care). Image interpretation will be based on guidelines derived from an international fluciclovine (¹⁸F) reader consensus meeting held in June 2014. All readers will undergo training in interpretation of fluciclovine (¹⁸F) scans, and will have a training set available for reference. The investigators will have access to all the conventional imaging and medical record information.

The summary of findings will be documented on the appropriate CRF, in addition to a conventional imaging report issued as per standard of care in the respective institution.

Primary endpoint

The primary endpoint of clinical impact of fluciclovine (¹⁸F) in affecting treatment decisions will be assessed by record of the revised treatment plan post fluciclovine (¹⁸F) PET/CT scan in comparison to the pre-scan intended treatment plan.

Secondary endpoints

Improvement in outcome of radical salvage treatment based on fluciclovine (¹⁸F) PET/CT being included in the assessment.

This will be assessed as the proportion of these patients who have a treatment response or treatment failure, using the following definitions:

1. Treatment response
 - a. ≥50% decline in PSA [5] ±
 - b. Radiological response
2. Treatment failure
 - a. Increase or <50% decline in PSA ±
 - b. Radiological progression

PSA threshold

The positive detection rate will be calculated for the overall cohort and across a range of PSA values, to determine the optimum PSA threshold for lesion detection.

Safety assessment

Safety will be assessed from data on the occurrence of adverse events (AEs) and changes in clinical laboratory tests, vital signs, injection-site status, and physical examination findings from the time of administration of fluciclovine (¹⁸F) injection throughout the study period. This has been described in detail in Section 9.

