5.4.2.2 PSA threshold

The detection rate (DR) will be calculated as number of positive fluciclovine (¹⁸F) scan results/total number of scans.

Date: 10OCT2018 Version: Amendment 1 Final

The point estimate (expressed in percentage) of the DR will be presented at the region level and at the subject level. These rates will be presented for all subjects from the FAS and PPS, overall and across a range of baseline PSA values:

- 0 0.2
- \bullet >0.2 0.5
- \bullet >0.5 1.0
- \bullet >1.0 2.0
- \bullet >2.0 5.0
- \bullet >5.0 10.0
- >10.0

to determine the optimum PSA threshold for lesion detection. See section 2 General Principles for baseline definition.

The detection rates will also be summarised across the following baseline Gleason score categories: <=6, 7, 8 and >=9.

All fluciclovine (18F) and other imaging results will be listed.

Handling of Dropouts or Missing Data 5.4.3

Subjects who withdrew from the study prior to completion will be summarised. Withdrawn subjects will not be directly replaced and no imputation of missing data will be conducted.

5.4.4 **Interim Analyses and Data Monitoring**

A single interim analysis of the primary endpoint will be performed in the first 85 evaluable subjects. If the number of treatment changes is greater than 45 (52.9%, with a 97.5% two-sided CI of 40.3%-62.3%, so the lower limit is over 40%), the trial will be terminated early due to overwhelming effectiveness. If the number of treatment changes is 8 or fewer (9.4%, with a 97.5% two-sided CI of 3.6%-18.9%, so the upper limit in this population is below the 20% of the null hypothesis), the trial will be terminated early due to futility.

Examination of Subgroups

No subgroup analyses will be conducted during the study.

Site Specific Sub-study 5.4.6

A site specific sub-study will be conducted in order to compare the ordered subset expectation maximisation (OSEM) standard of care method of reconstructing PET/CT images with that of the Bayesian penalised likelihood method of PET/CT image reconstruction. The analysis of the sub-study results is beyond the scope of this SAP.

SAFETY EVALUATION

All safety evaluations will be performed on the safety analysis set (SAF) unless specified otherwise.

Date: 10OCT2018 Version: Amendment 1 Final

All safety tables will be presented by centre and overall.

Subjects will be included and counted in summary tables only if they have available data.

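### Up to 1.0 ng/mL the entry rule admits almost only fast-doubling post-prostatectomy men, so crude detection rates compared across 1.0 mix PSA level with doubling time

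*Protocol*

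**What the plan says.** **Entry.** Protocol 6.2, criterion (2), has two routes.

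- After radiotherapy or brachytherapy: "Increase in PSA level ≥ 2.0 ng/mL above the nadir level after radiotherapy (RT) or brachytherapy". No doubling-time condition is attached.
- After prostatectomy: "EITHER two consecutive rises in PSA and final PSA > 0.1 ng/mL OR three consecutive rises in PSA". In addition, under (2)b.i, the man "should have a PSA doubling time of ≤ 15 months OR PSA level ≥ 1.0 ng/mL at time of recruitment". PSADT is calculated with a named online nomogram from at least two PSA values within 12 months of screening, taken after the last nadir.

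**Analysis.** Protocol 11.2 calculates the detection rate overall and "across a range of PSA values, to determine the optimum PSA threshold for lesion detection". SAP 5.4.2.2 carries this out: "These rates will be presented for all subjects from the FAS and PPS, overall and across a range of baseline PSA values". Of its seven bins, three lie at or below 1.0 ng/mL (0-0.2, >0.2-0.5, >0.5-1.0). There is one further breakdown: "The detection rates will also be summarised across the following baseline Gleason score categories". Detection is not split by PSADT or by prior prostatectomy, PSADT is not in the cancer-history summary of SAP 4.4.3, and SAP 5.4.5 plans no subgroup analyses. Neither document gives a rule for what makes a threshold optimal.

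**Kinetics.** Protocol 3.3 says that "the detection rate of choline PET/CT remains poor in the setting of relatively low PSA and slow PSA kinetics". It gives no figure for the kinetics part.

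**Data.** Protocol 7.5 provides that the dates and levels of each participant's "PSA from the date of radical therapy will be recorded".

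**The concern.** The two limbs of (2)b.i are alternatives, so the doubling-time limb bites only where the PSA limb fails, that is, below 1.0 ng/mL. The restriction on kinetics switches off at a point inside the PSA range in which the plan looks for a threshold. A reader comparing the >0.5-1.0 bin with the >1.0-2.0 bin would be comparing men who differ in doubling time as well as in PSA, and nothing in the plan separates the two.

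At stake is the second secondary objective, the PSA threshold for lesion detection, which the Protocol words for biochemical recurrence in general. If fast doubling makes a positive scan more likely at a given PSA, the low bins look better than they would for all post-prostatectomy men with that PSA, and the rise in detection with PSA looks shallower than it is.

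**Working it through.** **1. Figures in the plan.** The threshold analysis has no stated sample size, precision or estimate to reproduce. The only sample size is for the primary endpoint: n = 1.96² × 0.20 × 0.80 / 0.06² = 170.7, rounded up to 171, and 171 / 0.95 = 180. Both match Protocol 11.1. Neither bears on this point.

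**2. Who can be in each PSA range.** PSA cannot be negative, so nadir + 2.0 means at least 2.0 ng/mL when that criterion is met.

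| PSA at recruitment (ng/mL) | Post-prostatectomy | Post-radiotherapy or brachytherapy |
|---|---|---|
| below 1.0 | PSADT ≤15 months only | cannot qualify |
| 1.0 to below 2.0 | any PSADT | cannot qualify |
| 2.0 and above | any PSADT | can qualify, any PSADT |

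The three lowest SAP bins fall in the first row, with three small leaks:

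- A PSA of exactly 1.0 enters with any PSADT but is counted in >0.5-1.0.
- The bins use the latest PSA before injection (SAP section 2), which may differ from the PSA at recruitment.
- The full analysis set keeps every scanned subject, including eligibility deviations (SAP 4.1).

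**3. Size of the excess below 1.0.** All inputs here are assumptions. Let D be the detection rate at a given PSA over all doubling times, f the share with PSADT ≤15 months, and OR the odds ratio for detection, fast against slow, at equal PSA. Then

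- D = f × p_fast + (1 − f) × p_slow, with odds(p_fast) = OR × odds(p_slow)
- the trial sees p_fast, so the excess is p_fast − D = (1 − f) × (p_fast − p_slow)

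For D = 30% and f = 0.5:

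| OR | p_slow | p_fast (seen in the trial) | Excess (points) |
|---|---|---|---|
| 1 | 30.0% | 30.0% | 0 |
| 1.5 | 25.8% | 34.2% | 4.2 |
| 2 | 22.8% | 37.2% | 7.2 |
| 3 | 18.9% | 41.1% | 11.1 |
| 4 | 16.3% | 43.7% | 13.7 |

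Check at OR 2: 0.5 × (37.2 − 22.8) = 7.2. Over D = 20-40%, f = 0.4-0.7 and OR = 1.5-4, the excess runs from 1.8 points (D 20%, f 0.7, OR 1.5) to 19.6 points (D 40%, f 0.4, OR 4). It is zero at OR 1 throughout.

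**4. Effect on a threshold.** Because the plan defines no optimum, take as a stand-in the PSA at which detection reaches 30%. Assume a log-odds slope of 0.5 per PSA doubling, D = 40% at 1.0 ng/mL and f = 0.5.

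| OR | All doubling times (ng/mL) | As seen in the trial (ng/mL) |
|---|---|---|
| 1 | 0.54 | 0.54 |
| 1.5 | 0.54 | 0.41 |
| 2 | 0.53 | 0.34 |
| 3 | 0.52 | 0.26 |
| 4 | 0.51 | 0.22 |

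The same model at PSA 0.71 and 1.41, the geometric midpoints of the >0.5-1.0 and >1.0-2.0 bins, gives at OR 2 a rise of 34.4% to 45.9% for all doubling times but 42.1% to 45.9% in the trial. At OR 3 the true rise of 34.6% to 45.6% appears as a slight fall, 46.7% to 45.6%.

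**The case against.** **The bias is conditional.** A reader might infer that the threshold is simply biased. The documents do not support that. It requires PSADT to change fluciclovine detection at a given PSA. Protocol 3.3 offers one clause, about choline, which names low PSA and slow kinetics together; the detection figures around it are by PSA level. This stands: the entry logic is certain, the size is not known, and zero is possible.

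**Each bin is valid for the trial's own population.** Men meeting Protocol 6.2 are the study population, and the rate in each bin describes them correctly. This also stands. It does not rescue the comparison between bins, because the population changes in kinetics at 1.0, and a threshold is a comparison between bins.

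**No estimator is defined.** With no rule for the optimum, the downward pull acts on a descriptive reading of seven rates, and the documents do not say that a cut would be sought at 1.0. True, but the tables are stated to serve that purpose.

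**The low bins are not purely fast-doubling.** The leaks listed under the working mean that a claim about only fast doublers at or below 1.0 is too absolute. They are probably small.

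**Noise may exceed the shift.** Protocol 11.3 records that recruitment stopped early after the 85-patient interim. If subjects spread evenly over seven bins (an assumption), 85 gives about 12 per bin and a 95% half-width of 1.96 × √(0.35 × 0.65 / 12) = 27 points at 35% detection; 180 would give about 26 per bin and 18 points. That argues for intervals and modest claims, not for leaving a systematic difference in place.

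**A regression would not repair it.** Log PSADT is undefined when PSA is flat or falling, and with almost no slow doublers below 1.0 a model there would extrapolate. Agreed; a model is not asked for.

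**Conclusion.** The point holds in a limited form. The SAP bins up to 1.0 ng/mL consist almost entirely of post-prostatectomy men with PSADT of 15 months or less; higher bins also hold slow doublers and, from about 2.0 ng/mL, post-radiotherapy men. Crude detection rates compared across 1.0 therefore confound PSA level with doubling time, and with primary treatment higher up, and nothing in the plan handles this.

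If faster doubling raises fluciclovine detection, the gradient is flattened and an apparent threshold is likely pulled downwards. The ranges in the working rest on assumed odds ratios, shares and detection rates, none of which is in the documents, so they show what is possible and do not estimate the effect. The primary endpoint is untouched. The change is still worth making: it concerns a stated secondary objective, the cause is built into the entry rule, and the data to address it are already collected.

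**What to change.** In SAP 5.4.2.2, labelled post hoc if added after database lock (the second addendum already postdates it), and with SAP 5.4.5 adjusted to match:

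1. Derive PSADT for every post-prostatectomy subject from the recorded PSA history by the entry method, with a category for PSADT not calculable or PSA not rising.
2. Present detection rate by PSA bin, with exact 95% confidence intervals, for post-prostatectomy subjects with PSADT of 15 months or less. Base any comparison or threshold across 1.0 ng/mL on that table. Show subjects with PSADT above 15 months separately at PSA 1.0 ng/mL and above.
3. State that results for subjects below 1.0 ng/mL at recruitment apply to post-prostatectomy men with PSADT of 15 months or less. This follows from the entry rule and needs no assumption about effect size.

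The cost is one derived variable, one or two tables and a few sentences, with no new data or visits. The downsides are smaller cells, some subjects without a calculable PSADT, and a narrower claim below 1.0 ng/mL.
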